## 1 Overview

This document provides a detailed plan for Neqstent: **Coil Assisted Flow Diversion: A prospective, single arm, multi-center study to assess the safety and performance of Neqstent in adjunctive therapy (CAFI Study)**

## 2 Clinical Study Synopsis

Study Title	Coil Assisted Flow Diversion: A prospective, single arm, multi-center study to assess the safety and performance of Neqstent in adjunctive therapy (CAFI Study)
Study Purpose	Cerus Endovascular is sponsoring a prospective, single arm, multi-center study to document the safety and performance of Neqstent in adjunctive therapy. The purpose of the study is to document safety and performance of the Neqstent in adjunctive therapy in treatment for patients with intracranial aneurysms (IA).
Indications for Use and Intended Use	Neqstent is intended for use in conjunction with embolization coils for endovascular embolization of saccular intracranial aneurysms. The device should only be used by physicians licensed and credentialed to perform endovascular embolization catheterization procedures. Physicians must be thoroughly familiar and experienced with standard vascular embolization techniques and trained on the Neqstent before using the device.
Neqstent Training	Cerus Endovascular will provide training using flow models and didactic slide presentation. Physician proctoring will occur for the first three implants and an experienced Neqstent implanter will provide guidance over the identification of all the study patient aneurysms at each site to facilitate successful patient identification and implantation. A web-based image system called CIMAR will be used to view and store angiographic images of patient aneurysms or images will be viewed as forwarded by the treating physician.
Study Design	Prospective, single arm, multi-center study.

[figure not shown]

Clinical Investigation Plan

Title

*Confidential & Proprietary*

**Coil Assisted Flow Diversion: A prospective, single arm, multi-center study to assess the safety and performance of Neqstent in adjunctive therapy (CAFI Study)**

Study Size and Duration	
Study Size: The study population will include 51 subjects enrolled and implanted at up to 11 centers.
 
Study Duration: It is expected that the study will take 6 months to enroll a minimum of 51 patients. Follow-ups for the primary endpoint are the 6-month visit and 12-month visit, depending on the Raymond Roy score at the 6-month visit. Total duration of enrollment approximately 6 months, follow-up duration for primary endpoint (6-12 months), 24 months follow-up and reporting (3 months) will take approximately 33 months.
 
Any patient for whom a failed implant attempt is performed will be followed for 1 month, or until resolution of any potential device or implanted related adverse events, whichever occurs last.
 
Any patient who is consented but has no implant attempt will be study exited.

Device Description	
The Neqstent device works by providing a physical barrier between the parent vessel and the intracranial aneurysm neck (as demonstrated by the Neqstent clinical investigations as well as the pre-clinical research) thereby excluding the aneurysm from the parent artery blood flow. The Neqstent implant is sized to provide a proper fit and position across the neck of the aneurysm. Therefore, blood flow is diverted away from entering at the neck, leading to reduction in flow into the aneurysm cavity with subsequent stasis followed by the formation of thrombus within the confines of the aneurysm. As wound healing progresses and fibrosis occurs over the ensuing days and months, it serves to strengthen the physical barrier between the parent vessel and the aneurysm cavity. The weakened vascular tissue of the aneurysm cavity, in particular the dome, is thus protected from the shear wall stresses generated by the previous blood flow.
  
Figure 1 - Neqstent
 
The Neqstent (NQS) (NQS407-XX, NQS409-XX, NQS411-XX) is an intrasacular, self-expanding, embolization device intended for the treatment of intracranial aneurysms. The NQS is shown in Figure 1 and comprises an:
 
Implant
 
The implant is a self-expanding concave shaped device comprised of a double layer nickel-titanium and platinum wire mesh, and a platinum marker. The implant is packaged unconstrained in a protective dispenser hoop with an Introducer preloaded onto the DPW shaft just proximal to the implant.

Clinical Investigation Plan

Title

*Confidential & Proprietary*

**Coil Assisted Flow Diversion: A prospective, single arm, multi-center study to assess the safety and performance of Neqstent in adjunctive therapy (CAFI Study)**

Device Description (continued)	
Detachable Pusher Wire (DPW)
 
The DPW functions as a guidewire for implant delivery. The pre-attached DPW has a composite stainless steel and polymer construction, and a platinum marker. The DPW has a white fluoro-saver mark on its proximal shaft that provides a visual indication of when the implant is approaching, but not exiting the distal end of the micro-catheter (MC).
 
Introducer
 
The Introducer is a single lumen polymer tube that is used to constrain the implant during introduction into the micro-catheter hub. The implant body and proximal marker can be visualized under fluoroscopy.
 
All devices are provided sterile and nonpyrogenic and are for single patient use only. The device is not an active device and does not incorporate any software/firmware.
 
The Neqstent is offered in three sizes, suitable for embolization of intracranial aneurysm. Table 1 details the selection guideline for these three sizes:
 
The Neqstent should only be used by operators who have received appropriate training in neurointerventional techniques. The operator delivers the implant to the aneurysm under fluoroscopic guidance using standard endovascular techniques and a commercially available 0.027" inner diameter MC. The implant is electrolytically detached from the DPW using a commercially available detachable coil power supply.
 
Due to its unique placement across the neck of the aneurysm, the device acts as both a flow disrupter and diverter. The Neqstent only requires the neck diameter to be taken into consideration when sizing the implant to the aneurysm (please see figure below). The height is not a requirement as the dome of the aneurysm is not required to stabilize the device. The device mesh provides a uniform scaffold distributed across the neck of the aneurysm for the establishment of neointimal development and unlike devices placed in the parent vessel, is not dependent on the use of dual antiplatelet therapy.

---------------------------------------	--

**Table 1. Implant Size Selection Guide**

REF (Catalog Number) – Diameter	Aneurysm Neck (mm)
NQS407-XX – 7 mm	3.0 - 5.0
NQS409-XX – 9 mm	4.0 - 6.0
NQS411-XX – 11 mm	5.0 - 8.0

 Stryker Neurovascular Excelsior® XT-27® (0.027" ID, 2.9F/2.7F OD, 150cm Length)

 Detachable Coil Power Supply: Stryker Neurovascular InZone® Detachment System, REF M00345100940

 Power Supply Detachment Cable: Stryker Neurovascular IZDS Connecting Cable, REF 00345110250

Clinical Investigation Plan

Title

*Confidential & Proprietary*

**Coil Assisted Flow Diversion: A prospective, single arm, multi-center study to assess the safety and performance of Neqstent in adjunctive therapy (CAFI Study)**

Objective and Endpoints	
The primary objective of this study is to document the safety and performance of the Neqstent.
 
1. Primary Safety Endpoint:
 
The proportion of subjects with death of any non-accidental cause or any major disabling stroke within the first 30 days after treatment or major disabling stroke or death due to neurological cause from day 31 to 6 months after treatment.
 
Note: Major Disabling Stroke is defined as an episode of neurological signs or symptoms that persist beyond 24 hours accompanied with evidence of ischemia/infarction on imaging that results in an increase of NIHSS from baseline by <math>\geq 4</math> points and/or an increase from mRS baseline by <math>>2</math>.
 
2. Primary Performance Endpoint:
 
To demonstrate the occlusion rate on the 6 month angiogram as adjudicated by a core laboratory. Success will be defined as complete occlusion demonstrated by a Grade 1 using the Raymond Roy Scale.
 
Note: In the event of a Grade 2 or more using the Raymond Roy Scale, a second assessment will be made at 12 month follow-up to re-assess for remnant stability and/or complete occlusion and will be reported as a secondary efficacy endpoint.

Sample Size	51 subjects will be enrolled to obtain adequate follow-up data for the study to complete sponsor obligation to the notified body.
Number of Sites	Up to 11 sites will enroll in the study.
Study Visits	Baseline, procedure, discharge, one (1) month, six (6) months, twelve (12) months and twenty-four (24) months.

Clinical Investigation Plan

Title

*Confidential & Proprietary*

**Coil Assisted Flow Diversion: A prospective, single arm, multi-center study to assess the safety and performance of Neqstent in adjunctive therapy (CAFI Study)**

Enrollment and Eligibility	Enrollment
	
To participate, patients must meet all inclusion criteria and no exclusion criteria listed below. All patients must sign a study-specific consent form prior to the study procedure. Final qualification will occur during the study procedure due to the need for confirmation of IA appropriateness with cerebral angiography. The patient is enrolled at the time of consent and is considered a study subject in the reporting analysis group only when the patient is fully qualified and a Neqstent device has been placed into the patient's body. The following listing provides examples of patient enrollment scenarios for the study:
 

• The patient is not considered enrolled but not included in the primary analysis group in the study: if at the onset of the procedure in the initial DSA, the investigator determines the patient's IA was not suitable for treatment with the device, thus, no attempt was made by the investigator to place the device. The patient will be treated outside of the study per the investigator's usual practices. The reason for not treating the patient must be documented on a study exit form. The patient is not included in the primary analysis group because the Neqstent was never opened or deployed inside the patient. All patients will be listed in the final report.

• The patient is considered enrolled but not included in the primary analysis group in the study: at the onset of the procedure, the investigator determines the subject's IA was suitable for treatment with the device. The investigator attempted but was unable to place the device within the IA and the subject required alternative treatment. The subject is considered enrolled for the purposes of the study but will only be followed through the 1 month visit. All failed implant attempts will be reported in the final report.

• The patient is considered enrolled and included in the primary analysis group in the study: if at the onset of the procedure, the investigator determines the subject's IA was suitable for treatment with the device. The investigator successfully placed the device within the IA. The subject is considered enrolled for the purposes of the study and will be followed for the duration of the study.

 
The patient is considered enrolled and included in the primary analysis group in the study: if at the onset of the procedure, the investigator determines the subject's IA was suitable for treatment with the device. The investigator successfully placed the device within the IA. In addition, the subject required and received further treatment with another endovascular device(s). The subject is considered enrolled for the purposes of the study and will be followed for the duration of the study.


Clinical Investigation Plan

Title

*Confidential & Proprietary*

**Coil Assisted Flow Diversion: A prospective, single arm, multi-center study to assess the safety and performance of Neqstent in adjunctive therapy (CAFI Study)**

Eligibility Criteria	
Patients of all genders who meet all indications and contraindications will proceed to implantation.
 
Inclusion criteria
 

1. Patient's indication for treatment of unruptured IAs according to the national/international guidelines.

2. Age 18-80 years at screening

3. Patients who are suitable for non-emergency endovascular embolization of saccular IAs

4. IA located at a bifurcation in the anterior or posterior circulation with dimensions consistent with implant size selection guidelines included in the IFU

5. Patient has the necessary mental capacity to participate and is willing and able to participate in the study for the duration of the study follow-up and is able to comply with study requirements

6. Patient able to give their informed consent can be included in this study. This must be demonstrated by means of a personally signed and dated informed consent document indicating that the subject has been informed of and understood all pertinent aspects of the study.

 
Exclusion criteria
 
The presence of condition that may create unacceptable risk during the aneurysm embolization procedure, such as patients with:
 

1. Ruptured aneurysm

2. Patient anatomy or physiology considered unsuitable for endovascular treatment

3. Any patient anatomy, physiology, existing implants with failed aneurysm embolization that would interfere with the ability for Neqstent to seal at the neck of the aneurysm. (i.e., compacted coils in close proximity to the neck that prevent good apposition of the Neqstent to the wall of the aneurysm, stent and/or stent-like devices whose struts span the aneurysm neck to retain the coil mass that inhibit access and/or successful Neqstent seating at the aneurysm neck, and/or any aneurysm that has a failed device and confirmed thrombus-burden inside the aneurysm sac)

4. Contraindication for arterial access

5. Largest measured IA neck diameter <math>>8</math> mm or <math><3</math> mm

6. Target IA contains other devices/implants (e.g., coils) that will prevent complete expansion of Neqstent

7. Known allergy to platinum, nickel or titanium

8. Known allergy to contrast agents

-----------------------------	---

Clinical Investigation Plan

Title

*Confidential & Proprietary*

**Coil Assisted Flow Diversion: A prospective, single arm, multi-center study to assess the safety and performance of Neqstent in adjunctive therapy (CAFI Study)**

9. Contraindication to anticoagulants or platelet inhibitor medication
10. Stenosis of the target IA's parent vessel >50%
11. Anticoagulation medications such as warfarin that cannot be discontinued.
12. Pregnant, breastfeeding or women of childbearing potential not on adequate birth control (only women with a highly effective method of contraception [oral contraception or intra-uterine device] or sterile women can be enrolled to the study)
13. Acute / chronic renal failure (including dialysis); Creatinine > 2.00 mg/dl or > 182  $\mu$ mol/L
14. Myocardial Infarction, Stroke or TIA within the last 6 months
15. Any other medical issue within the brain that precludes the device implantation such as brain surgery, radiation in the target area of intervention, acute traumatic craniocerebral injury, etc.
16. Other medical conditions that cause an inability to comply with study requirements and/or that could increase the risk of neurovascular procedures or death within 2 years (e.g., liver failure, cancer, heart failure, chronic obstructive pulmonary disease, immunosuppression, neural disease, and hematologic disorders etc.)
17. Participating in another study with investigational devices or drugs that would confound the effects of the study outcomes
18. The presence of condition that may create unacceptable risk during the aneurysm embolization procedure

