Incomplete occlusion has additional risks. Incomplete occlusion of IAs can lead to IA growth and reopening related to continued pulsatile blood flow into the IA. Moreover, coils can become compacted and regress into the dome of the IA, resulting in further filling at the IA neck. In addition to exposing patients to bleeding risk, incomplete IA occlusion is also associated with the need for surveillance cerebral angiography and retreatment. Retreatment procedures can be complex and not always successful, thereby exposing the patient to further risk.

Recently, a new set of devices for IA treatment have become available. These devices, called flow diverters, are placed either in the parent artery or in the IA itself. Flow diverters have a mesh component that retards the flow of blood from the parent artery into the IA fundus. Stasis of blood in the fundus induces IA thrombosis, which achieves the goal of preventing pulsatile flow into the IA. The mesh component of flow diverters has also been shown to serve as a scaffold for endothelial growth, which can promote permanent occlusion of the target IA. These two components (flow disruption and scaffolding for re-endothelialization) distinguish flow diverters from standard coils embolization. For large (>10 mm in maximum dimension) and giant (>25 mm) IAs, flow diverters have been shown to have high complete occlusion rates Most flow diverting devices are placed into the parent artery, requiring the patient to take antiplatelet agents (aspirin and clopidogrel) for prolonged periods. This can be a significant limitation, which precludes their use in the acute setting of aneurysm treatment.

Most flow diverting devices are placed into the parent artery; this requires the patient to take antiplatelet agents (aspirin and clopidogrel) for prolonged periods. The Neqstent device (Cerus Endovascular, Oxford, UK) is designed to be a flow diverter that is placed instead into the IA sac. Like other flow diverters, the device is designed to disrupt blood flow into the IA and to act as a scaffold upon which endothelial cells can grow. These two mechanisms of action may increase the likelihood of complete IA occlusion compared to embolization coils. Because the device is placed into the IA sac, antiplatelet therapy is not required. Use of antiplatelet and/or anticoagulation is at the discretion of the treating physician.

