## 10.2 Patient Population

Two patient populations will be considered in the analyses, an Intent-to-Treat (ITT) population and a Per Protocol population (PP). The ITT population includes all patients. The PP population will include subjects who complete 6 months of follow-up, die prior to their 6-month clinic visit, or are study failure (withdrawal from study to obtain alternate treatment). The PP will exclude patients with any major protocol violation that affects proper study inclusion or significant outcomes. Endpoints will be evaluated in the PP and ITT populations.

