## 10.6 Sample Size Rationale and Statistical Considerations

This is a single arm study designed to provide adequate data for the purpose of a pre-market study. It is expected the 51 patients with evaluable data at 6 month and 12 month follow-up (where necessary) will show adequate evidence of safety and performance of Neqstent device.

For the purpose of sample size calculation, the primary outcome measurement is assumed to be the composite of the listed primary endpoint components.

Extensive literature search was conducted to gather information on the non-inferiority margin. Due to limited results found in literature, the non-inferiority margin for this study,  $\delta = 10\%$ , was chosen to align with the study design.

The sample size estimation was based on the following assumption:

- Success rate of the investigational is expected to be 70%
- Success rate of standard treatment is estimated to be 55%
- Power is set at 80% and one-sided significance level is set at 5%
- Expected rate of attrition is 10%

Based on the assumptions, a total of 46 subjects are required to show that the expected success rate of 70% is different than the true rate of 55% with a delta of 10%. Adding in additional subjects for anticipated loss to follow-up, 51 subjects are needed to be enrolled for a total of 46 subjects with 6 month data.

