#### **Endpoint Analysis:**

The primary performance endpoint will be calculated as the proportion of subjects with complete occlusion demonstrated with a Grade 1 on the Raymond Roy Scale at 6 months follow-up. In the event of a Grade 2 or more using the Raymond Roy Scale, a second assessment will be made at 12- month follow-up to re-assess for complete occlusion and will be reported as a secondary efficacy.

For AE reporting, both subject counts and event counts will be presented in tabular summaries of results.

A summary of subjects with protocol deviations will be reported but those subjects will be included in all analyses although endpoints may be summarized without the subjects (per-protocol analysis group) to provide additional information but not for the primary analysis.

For continuous variables, statistics will include means, standard deviations, medians and ranges. Categorical variables will be summarized in frequency distributions. Missing data will not be imputed. The number of data values available for each analysis will be reported so that the impact of missing data can be seen.

Statistical analyses will be conducted in SAS version 9.4 or above (SAS Institute, Cary, N.C.).

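### The 12-month secondary occlusion endpoint has no rule for target aneurysms retreated after the index procedure and no stated denominator

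*Combined protocol and SAP*

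**What the plan says.** The primary performance endpoint is core-laboratory Raymond Roy Grade 1 on the 6-month angiogram. For subjects graded 2 or more, the Note in the synopsis (Section 2, Objective and Endpoints) adds that "a second assessment will be made at 12 month follow-up to re-assess for remnant stability and/or complete occlusion", reported as a secondary efficacy endpoint. Section 10.4.1 repeats this with "or" in place of "and/or". Section 10.6, Endpoint Analysis, mentions only complete occlusion: the 12-month look is to "re-assess for complete occlusion and will be reported as a secondary efficacy". Section 7.9 confirms that the 12-month angiogram is taken only in this group. Remnant stability is not defined anywhere.

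Three other statements bear on retreatment:

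- Section 4 accepts that "incomplete IA occlusion is also associated with the need for surveillance cerebral angiography and retreatment".
- Section 10.2 keeps in the Per Protocol (PP) population a subject who is a "study failure (withdrawal from study to obtain alternate treatment"). The same sentence lists subjects who complete 6 months of follow-up or die before the 6-month visit.
- Section 10.6 analyses primary and secondary endpoints in an intent-to-treat (ITT) population using whatever data are available, and states: "Missing data will not be imputed".

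No section says how a target aneurysm retreated after the index procedure is scored at 12 months.

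**The concern.** The 12-month assessment selects the subjects whose aneurysms were not fully closed at 6 months. By the plan's own account, incomplete occlusion is associated with retreatment. The assessment then grades whatever the 12-month angiogram shows.

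Two things can happen to a subject retreated between the two angiograms. If the subject stays in the study and the aneurysm is graded 1, the text as written reports complete occlusion. If the subject withdraws to be treated elsewhere, there is no 12-month grade, none is imputed, and a subject known to have been incompletely occluded at 6 months leaves the ITT rate. Compared with scoring retreatment as non-success, the first route raises the rate, and the second raises it whenever at least one remaining subject closes.

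This is a single-arm, descriptive study that relies on clinical judgement of the reported proportions (Section 10). Section 10.6 also expects evaluable data at 6 months, and at 12 months where necessary, to show adequate evidence of performance. A 12-month proportion that mixes occlusion after Neqstent with coils and occlusion after a second treatment is hard to interpret. Without a rule, the choice would be made after the data are seen.

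**Working it through.** **Inputs.** From Section 10.6: 46 evaluable subjects of 51 enrolled, 70% expected success, 55% for standard treatment, margin 10%, power 80%, one-sided 5%, attrition 10%. The documents give no retreatment rate and no rate of unaided late closure, so both are assumed below.

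**The plan's own figure.** The non-inferiority formula for two proportions, per arm, gives

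n = (1.6449 + 0.8416)² × (0.55 × 0.45 + 0.70 × 0.30) / (0.70 − 0.55 + 0.10)² = 6.183 × 0.4575 / 0.0625 = 45.26, rounded up to 46.

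Adding 10% gives 46 × 1.10 = 50.6, or 51. The 46 is thus reproduced as the size of one arm of a two-arm comparison. That is a separate matter; here 46 serves only as the count of evaluable subjects.

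**How many enter the 12-month look.** At 70%: 46 × 0.30 = 13.8, about 14. At 55%: 46 × 0.45 = 20.7, about 21.

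**Effect of one retreated subject credited as Grade 1.** 1/14 = 7.1 points; 1/21 = 4.8 points. In a cumulative rate over all evaluable subjects, 1/46 = 2.2 points.

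**Effect over a range.** Assume 3 subjects close without retreatment. Let r be the number retreated, with every one of them reaching Grade 1 where they stay in, or every one withdrawing where they leave. With m subjects in the look, the rates are (3 + r)/m if credited, 3/(m − r) if they withdraw and are dropped, and 3/m if retreatment is non-success.

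| In the look | r | Credited | Dropped | Non-success |
|---|---|---|---|---|
| 14 | 0 | 21.4% | 21.4% | 21.4% |
| 14 | 2 | 35.7% | 25.0% | 21.4% |
| 14 | 4 | 50.0% | 30.0% | 21.4% |
| 14 | 6 | 64.3% | 37.5% | 21.4% |
| 21 | 0 | 14.3% | 14.3% | 14.3% |
| 21 | 2 | 23.8% | 15.8% | 14.3% |
| 21 | 4 | 33.3% | 17.6% | 14.3% |
| 21 | 6 | 42.9% | 20.0% | 14.3% |

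If no subject closes unaided, dropping has no effect (0% either way), while crediting 4 of 14 still gives 28.6%.

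**Cumulative 6-or-12-month rate, r = 4.** With 32 successes at 6 months: 39/46 = 84.8% credited, 35/42 = 83.3% dropped, 35/46 = 76.1% non-success. With 25 successes at 6 months: 32/46 = 69.6%, 28/42 = 66.7%, 28/46 = 60.9%.

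**Does Section 10.2 settle it?** A subject who leaves at, say, month 8 has already completed 6 months and so meets the follow-up condition for PP in any case. The study-failure label decides membership of a population; it assigns no 12-month outcome. It does not mention ITT scoring, nor a retreated subject who stays in the study.

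**The case against.** The strongest reply is that the plan is silent rather than wrong. A reader might infer that it has a rule crediting retreatment to Neqstent. It does not: it says only that the aneurysm is re-assessed and reported, and crediting is the default reading of that silence. The enrolment scenarios in Section 7.5 do keep subjects who received another endovascular device, but they describe the index procedure and do not settle later retreatment.

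A reader might also infer that anyone who leaves for retreatment vanishes from every analysis. That goes too far. Exclusion follows for ITT; Section 10.2 keeps such a subject in PP under a failure label, and how PP would score that subject at 12 months is unclear. Section 10.6 also promises the number of values behind each analysis, and Section 7.10 requires withdrawal reasons to be documented. The loss would be visible, though not corrected.

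Nor do the documents say that the 12-month look is meant to show remnants closing unaided. The stated aim is remnant stability and/or complete occlusion, for a device studied as adjunctive therapy. Reporting the observed grade with a count of retreatments would be another defensible choice, but the plan does not state that either.

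The scale is also uncertain. Section 4 says that incomplete occlusion brings surveillance as well as retreatment, and that retreatment does not always succeed. There may be few or no cases. The study is not powered, and the 12-month result has no threshold. The case report forms are not shown, so whether retreatment is recorded cannot be judged.

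What stands is that the endpoint lacks both a retreatment rule and a denominator, and that the literal reading favours the device.

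**Conclusion.** The point holds for the 12-month secondary endpoint, and the text should be changed before those data are analysed. Grading the 12-month angiogram without a retreatment condition, together with available-case ITT analysis, gives a rate that is too favourable if any retreated subject is credited, or if any is dropped while others close.

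Each credited subject is worth 7.1 points of about 14 subjects, 4.8 of about 21, or 2.2 of all 46. These figures rest on the plan's planning rates. The larger shifts in the table rest on assumed numbers of retreatments and unaided closures; with no retreatment the effect is nil.

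It would be tempting to extend this to the primary result, since the synopsis (Study Size and Duration) and Section 11.5 list the 12-month visit under follow-up for the primary endpoint. The endpoint definitions do not support that. The synopsis Note, Section 10.4.1 and Section 10.6 all make the 12-month result secondary, and events after the 6-month angiogram cannot change the 6-month grade. Neither the primary rate nor the sample size is affected.

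**What to change.** In the synopsis Note, Section 10.4.1 and Section 10.6:

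- Define the 12-month secondary efficacy endpoint as Raymond Roy Grade 1 without any retreatment of the target aneurysm after the index procedure.
- State the denominator as all subjects with Grade 2 or more at 6 months.
- Score retreatment, or withdrawal to obtain alternate treatment, before the 12-month angiogram as non-success in both ITT and PP.
- Report the number retreated and their post-retreatment grades separately.

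In the same edit, make the three descriptions of the 12-month look agree. If remnant stability is kept, define it. Reconcile the duration text that places the 12-month visit under the primary endpoint.

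The change is to wording only and adds no visits or imaging. Its cost is a somewhat lower 12-month rate. It governs how outcomes are scored and proposes no rule on when to retreat.
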